- **Impulsivity.** The 30-item Barratt Impulsivity Scale (BIS)⁷⁶ assesses general impulsiveness at all interview timepoints on six first-order factors (attention, motor, self-control, cognitive complexity, perseverance, and cognitive instability impulsiveness) and three second-order factors (attentional, motor, and non-planning impulsiveness). The BIS was validated among community, clinical, and correctional samples ($\alpha=.79-.83$).
- **Aggression.** The 12-item Brief Aggression Questionnaire (BAQ)⁷⁷ evaluates physical aggression, verbal aggression, anger, and hostility at all interview timepoints. The BAQ has stable test-retest reliability and convergent validity with behavioral aggression measures.
- **Housing.** A 7-item housing measure will assess housing stability at all post-release timepoints. Sample items include, “Have you had to “double up” with friends or relatives?”, “Do you consider yourself homeless?”, and “Where are you living or staying now?”
- **Employment.** A 10-item employment measure assesses employment at all interview timepoints. During the initial in-prison interview, the participant will be asked to think about their employment six months prior to their current incarceration. In all post-release interviews, the participant will be asked to reflect on their employment in the previous three months. Sample items include, “What was your work situation right before your current incarceration/over the past 3 months]?” and “How long have you been at your current employment?”

- Recidivism. Recidivism data on arrests in Florida, incarceration in a Florida state prison, the number of days to arrest or incarceration, and the reason for incarceration (i.e., commission of new crime or violation of the terms of release) will be collected from FDC and Florida Department of Law Enforcement databases annually for three years.

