18.0 Provisions to Protect the Privacy Interests of Subjects

18.1 Research participants are not ever required to meet with somebody whom they do not want to interact. If the participant would like a different interviewer, or a different person to facilitate the TARGET sessions if they are in the treatment group, then the research team will grant them that wish if possible. The participant will be informed at consent, and reminded throughout the study, that they can choose to stop any interview or intervention session at any time without any consequences or repercussions whatsoever. The participant has the option to not answer any questions that they find too personal and do not want to share with the interviewer. This information is all discussed with the participant during the informed consent process at the beginning of the study.

18.2 Research team members are trained in interviewing skills, including how to talk with the research participant in an empathic manner that helps put them at ease, which is particularly important considering the sensitive nature of some of the questions. Regarding the TARGET program for those in the treatment groups: all of the interventionist are trained counselors who are trained in working clinically with participants and have experience talking with our research participants in an empathic manner.

18.3 The only information the research team will access that does not come directly from the participants are the administrative data collected from department of corrections databases. This includes the following:

Commented [A3]: Are these all applicable?

- race/ethnicity
- release dates;
- type and length of supervision being released into;
- if you are on court mandated treatment during incarceration or post-release, and what type of treatment is required;
- custody levels at initial assignment and release;
- prison identification number;
- date of birth;
- both community and institutional (at time of entry into facility and final) risk scores, and which assessment tool is used;
- treatment and program participation;
- Protected Health Information from the Department of Corrections database;
- criminal history, including length of sentence, number of priors, age of first arrest, age at present offense, list of convictions, and what you are serving your current sentence on;

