- recidivism data, including dates and number of: rearrests resulting in a 48 hour stay, jail time, incarceration for a new conviction, re-incarceration from state prison for a new offense or technical violation, residential sanction facility;
- technical violations, including what the violation was and the result of violation;
- sanctions, including type, number received and reason for sanction;
- education level at admission and at release;
- employment status on admission and for those on parole;
- home plan upon release and housing status for those already released;
- program treatment referral or receipt by parole, including your need, services received and services completed

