Power analysis. To determine the sample size, we conducted an a priori power analysis with the software program G*Power. We conducted the power analysis to make sure we would be able to detect differential effects on key mechanisms of change and community stability between participants allocated into the two study conditions. We powered the study based on conducting multivariate analysis using ANCOVA. We used a small effect size estimate - Cohen's d of .15 - based on guidance and data from the Clinician Administered PTSD Scale on a similar population.⁶⁷ Being able to detect small effects is important as we may find minimal difference between group members. Using an alpha of .05 and powered at a .80 level across two groups with up to seven covariates, a sample of 352 would allow us to detect small effects. Thus, a targeted sample size of 400 provides statistical power greater than .80, giving us strong confidence that we will be able to detect even small difference between study conditions.

Recidivism. Survival analysis will be conducted to analyze time-to-event on recidivism outcomes (i.e., time to arrest and time to incarceration). Participants without the occurrence of the events will be censored at their last known event-free time point. Survival curves will be constructed using Kaplan-Meier estimates. Using the Kaplan-Meier curve allows us to derive the median, or that time at which 50% of cases of the event of interest has occurred, and the mean (i.e. the average time it took for the event to occur). Although there are several methods available to analyze time-to-event curves, the proposed study uses a Cox proportional hazard model which is a regression method for survival data and has been used in previous criminal justice-related studies. The Cox model allows for the identification of differences in survival rate due to study condition and prognostic factors, such as covariates. Further, the Cox model provides an estimate of the hazard ratio and its confidence interval. There are two underlying assumptions of the Cox proportional hazard model: (1) the hazard ratios of two people are independent of time and (2)

are valid only for time independent covariates. For the current study, results will be displayed for comparison of survival distributions for three years post-release.

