Power Analysis. The Bureau of Justice Statistics (BJS) 2005-2014 data show that 76.5% of prisoners age 24 or younger released in 2005 were arrested within three years of release. Specifically, 51.8% were arrested within the first year, an additional 17% in the second year, and an additional 7.7% in the third year. Our goal is to reduce recidivism by 28% over three years. Using these data and the method described by Collett (2003, pp. 299-312), we calculate that the hazard ratio of recidivism for this study at 1.39, meaning that members of the control group will recidivate 39% faster than participants receiving the targeted treatment. Using the same BJS data, we calculated the median survival time (pre-recidivism) for members of the control group at 17.28 months. The median survival time suggests that 50% of the control group will recidivate by 17.28 months after release from incarceration. These data provided the basis for the power calculation. The power analysis was conducted using PS software.⁷⁸ Results show that for a study with 200 experimental participants and 200 control participants, a hazard ratio of recidivism of 1.39, and a median survival time for the control group of 17.28 months, we will be able to reject the null hypothesis that the treated and control survival curves are equal with a probability (power) of .810. The Type I error probability associated with this test of this null hypothesis is 0.05. Therefore, the study will have adequate statistical power.

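### Recidivism is seen only in Florida records, and the undefined last event-free date lets men who die or leave the state stay in the risk set

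*Protocol*

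**What the plan says.** - **Events.** Protocol 5.0, Recidivism measure (under the item numbered 6.5), defines the data as "Recidivism data on arrests in Florida, incarceration in a Florida state prison, the number of days to arrest or incarceration", and these "will be collected from FDC and Florida Department of Law Enforcement databases annually for three years".
- **Censoring.** SAP, Recidivism: "Participants without the occurrence of the events will be censored at their last known event-free time point". The text does not say what establishes that date.
- **Horizon.** In the same SAP paragraph, "results will be displayed for comparison of survival distributions for three years post-release".
- **Other records.** Protocol 18.3 says that the only information not coming from participants "are the administrative data collected from department of corrections databases". The fields include "type and length of supervision being released into" and "home plan upon release and housing status for those already released". Neither a date of death nor a date of leaving Florida or transferring supervision is listed.
- **Direct contact.** Protocol 8.1 recruits men about four to six months before release and keeps them in the study for at most 18 months.
- **Power.** SAP, Power Analysis for recidivism, gives .810 for 200 men per arm, a hazard ratio of 1.39 (control to program), a control median of 17.28 months and a Type I error of 0.05. It contains no term for loss of coverage.

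**The concern.** A recidivism event can be recorded only while a man is alive and within reach of Florida records. Direct contact ends at most 18 − 6 = 12 to 18 − 4 = 14 months after release. For the remaining 22 to 24 of the 36 months, state records are the only source. A search of those records returns nothing for a resident who has not been arrested, and nothing for a man who died or moved away in month 4. If the last event-free date is taken as the date of the last extract, which is the easiest working reading, the second man stays in the denominator with no chance of an event.

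Two things are at stake. Both three-year curves would understate recidivism, increasingly so with time. And if departure or death differs by arm, the hazard ratio is biased. Such a difference is plausible, because only the program arm receives the study's housing and employment help and its community sessions (up to 10 or 15; the protocol gives both). Analysts cannot repair this afterwards unless the dates were requested.

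**Working it through.** **1. The plan's own power.** Take exponential survival, control hazard ln 2 / 17.28 = 0.0401 per month, program hazard = control / 1.39, and two-sided alpha 0.05 (the SAP does not state the sides).

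- Fixed 36 months: 76.4% of controls and 64.6% of program men have an event. Events = 200 × (0.764 + 0.646) = 282. Power = Φ(ln 1.39 × √282 / 2 − 1.96) = .790.
- With 18 months of accrual (protocol 8.2) plus 36 months: 311 events, power .828.

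The stated .810 lies between the two. The SAP does not give the accrual and follow-up times that were entered, and the figure is not disputed here.

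**2. Model for loss of coverage.** The SAP's cumulative arrest figures of 51.8%, 68.8% (51.8 + 17) and 76.5% give yearly control hazards:

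- year 1: −ln(0.482) = 0.730
- year 2: −ln(0.312 / 0.482) = 0.435
- year 3: −ln(0.235 / 0.312) = 0.283

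The program hazard is 0.72 times these (1 / 1.39 = 0.72). With no loss there are 282 events and power is Φ(|ln 0.72| × √282 / 2 − 1.96) = .788.

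**3. Adding loss.** Death or departure is given a constant yearly rate μ, independent of arrest risk within each arm. The rates are **assumed**, because the documents give none. The recorded-event density in an arm is f(t) = kλ(t) exp(−kΛ(t) − μt), with k = 1 for control and 0.72 for program. The large-sample Cox hazard ratio θ solves

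∫ [f_P (1 − π) − f_C π] dt = 0, with π = θY_P / (θY_P + Y_C).

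- Loss unrecognised: Y(t) = 1 − F(t), so lost men stay at risk to month 36.
- Censored at loss: Y(t) = exp(−kΛ(t) − μt).

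| Loss per year, program / control | Events | HR, loss unrecognised | HR, censored at loss | Power, censored at loss |
|---|---|---|---|---|
| 0 / 0 | 282 | 0.720 | 0.720 | .79 |
| 3% / 3% | 275 | 0.724 | 0.720 | .78 |
| 5% / 5% | 270 | 0.726 | 0.720 | .77 |
| 10% / 10% | 259 | 0.731 | 0.720 | .75 |
| 2% / 5% | 274 | 0.753 | 0.720 | .78 |
| 5% / 2% | 274 | 0.697 | 0.720 | .78 |

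**4. Size within the curve.** At 5% a year unrecognised, about 3%, 11% and 20% of the control time counted as at risk in years 1, 2 and 3 is unobservable. The control three-year rate reads 73.3% instead of 76.5%.

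**5. Check on the survival shape.** With the exponential model of step 1, 5% control and 2% program loss gives a control-to-program ratio of 1.307 (1 / 1.307 = 0.77). The reverse gives 1.454 (1 / 1.454 = 0.69). Censoring at loss returns 1.390 in both. The pattern does not depend on the shape chosen.

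**The case against.** **A reader might infer that the plan counts every event-free man to three years and scores him as a success.** The documents do not say so. The SAP has a censoring rule, three years is the span over which curves are shown, and a censored man is not a success in a Kaplan-Meier or Cox analysis. The defect is narrower: the censoring date is undefined, and the listed data cannot identify the men whose date should be earlier.

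**A reader might also infer that the arrest rates behind the .810 count arrests in any state, so that they describe a different endpoint.** The SAP quotes the percentages without saying which arrests they cover. That inference has no support in the documents.

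**Equal loss matters little.** This stands. At 5% a year in both arms the hazard ratio moves from 0.720 to 0.726. Power is .749 if loss goes unrecognised and .770 if it is censored, so the rule recovers about two points. The rest is events that no rule restores.

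**Unequal loss is assumed.** This also stands. No passage gives a rate or a difference by arm, and the bias can hide a benefit or exaggerate one. That uncertainty over direction is a reason to fix the rule before outcome data are seen.

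**Some protection exists.** Men must plan to live in one of four Florida counties, the SAP plans participant tracking, most of the expected arrests fall in year 1 (51.8 of 76.5 points), and housing status is among the requested fields. These limit early loss. But the housing field is not tied to censoring, and interview contact ends well before month 36.

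**Conclusion.** The concern holds in a limited form. The SAP does not say how the last event-free date is set from Florida-only records, and the listed data contain no date of death or out-of-state transfer. Men lost to coverage can therefore remain in the risk set to the last extract.

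Under assumed equal loss of 3% to 10% a year the hazard ratio changes by about 0.01 or less. Under assumed unequal loss of 2% and 5% it reads about 0.75 or 0.70 instead of 0.72, depending on which arm loses more. Censoring at loss removes the bias, provided that loss dates are recorded and loss is independent of arrest risk within each arm.

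Recidivism is a secondary objective. This is a correction worth making before the records are requested, not a flaw that invalidates the comparison.

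**What to change.** 1. **SAP, Recidivism.** Define the censoring date for event-free men as the earliest of: death; documented transfer of supervision or move out of Florida; the date through which the records are complete; three years after release. State that the Cox model then estimates a cause-specific hazard, with death as a censoring event.
2. **Protocol 18.3.** Add date of death and date of out-of-state supervision transfer to the record request. Use only these record-based dates in the main analysis, because they are obtained the same way in both arms.
3. **Sensitivity analysis.** Repeat the analysis with moves learned from interviews or from corrections housing status.
4. **SAP, Power Analysis for recidivism.** State that the .810 assumes no loss of coverage. With correct censoring and an assumed 3% to 10% lost a year, power is about .75 to .78, against .79 for the same model with no loss.

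**Cost.** A defined censoring rule, two fields in a request already planned, one extra analysis and one sentence on power. Counted follow-up falls slightly, the stated power is a little less favourable, and some unrecorded moves will still be missed.

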6.0 Data and Specimen Banking*

- 6.1 Collected data is stored in REDCap, and research team members and data analysts have access to the system. Data is protected and HIPPA compliant. Data collected is the interview assessment data using the tools listed in 6.4 for the initial interview and the 3 follow-up interviews.

7.0 Sharing of Results with Subjects*

N/A

8.0 Study Timelines*

- 8.1 *Describe*: Individuals will be recruited approximately four to six months prior to release and then we will remain in contact with them to collect primary data from them for 9 months after the conclusion of the intervention. Thus, participants can end up being engaged with the study for a maximum amount of 18 months.

Research Activities	Related Timelines
Recruitment of Study Participants:	May 2020-October 2021
Programming inside facilities:	June 2020-December 2021
Community Programming:	September 2020 -March 2022
TI (Completion of programming period):	November 2020-March 2022
T2 (3 Months post completion of program period)	February 2021-June 2022
T3 (9months post completion of program)	August 2021-Ducember 2022

- 8.2 Based on a recruitment goal of 400 and the number of staff and students that will be used to recruit study participants, it is anticipated that it will take eighteen months to enroll all study subjects into the study.

9.0 Subject Population*

Commented [A1]: Eligibility : Age, Risk Factor Identification (spectrum?), Screening for Lifetime Traumatic Experiences, Conversational English, Cognitive Consent, Release to Leon or Duval

Random Number generator (randomization)

9.1 Participant inclusion requirements include: (1) male; (2) age 18-35; (3) identified as having risk for recidivism; (4) screened as experiencing at least one LTE; (4) releasing from incarceration to one of our four study counties within six months; (5) conversational English; and (6) being able to cognitively consent into study participation.

9.2 Participants may be excluded if: they (1) identify as women; (2) younger than 18 or older than 35; (3) no demonstrated any risk; (4) not cognitively able to understand what it entails to be a research participant.

10.0 Vulnerable Populations*

10.1 The research team has reviewed the checklist relating to studies involving incarcerated individuals and have designed the study to be in consideration of these guidelines for the population.

11.0 Local Number of Subjects

11.1 400 individuals will be recruited into the study to participate. Participants will be returning to the following four county area: Leon, Columbia, Duval, and Suwanee.

12.0 Recruitment Methods

12.1 In order to enroll participants into the study, the research team will obtain regular lists of prospective participants from the Florida department of corrections (FDC) in each state. The list includes the name, age, sentencing county, prison location, scheduled release date, risk score, and offense history so that research team members can randomly identify prospective study participants. Then, the research team member emailed the primary contact person at each prison site the list of prospective participants' names and DOC ID numbers using a password protected and encrypted Excel database to schedule individual information and screening sessions.

The primary contact person at each prison site nor any other correctional official has a role in selecting the prospective participants that will be eligible for an information and screening session. Researchers schedule days to meet with prospective participants at the prisons. On those days, researchers will arrive at the prison and will meet with corrections officials to confirm with the official the names of those participants that the researchers met with to tell them about the study. Every member of the research team will be trained in the Prison Rape Elimination Act (PREA).

The day of the visit for recruitment, the correctional official can say that the visitor is from the Florida State University, but otherwise will not tell the prisoner that the visitor is there to see him/her about a research study. The prisoner can refuse to meet with the visitor. We do not want the correctional officer talking to the prisoner about

the study for several reasons: a) reduce potential for coercion; b) because it is not feasible to train all correctional officers in the prison on research protocol; and c) to protect confidentiality of the prospective participant.

Once the prisoner arrives to the visit in a private meeting room, the researcher will tell the prisoner about the study. The private room is one in which correctional officers may be able to see into the room for security purposes, but they cannot hear the content of the meeting. First, the researcher will confirm whether the returning prisoner intends to live in one of the designated study counties. Those individuals who do not intend to live in a study county will be thanked for their time and told they are not eligible for study participation.

The researcher will conduct consent procedures. The researcher will read aloud the consent form and allow for participants to have time to read the consent form on their own. The researcher will assure participants that their supervision will not be affected by their choice to participate or not participate in the study. The participants will also be told they can discontinue the study at any point or refuse to answer any questions without consequence. The benefits and risks of the study will be reviewed as will the expectations and limitations to breaches of confidentiality. Participants will be provided with two copies of the consent form – one for the participant to sign, either esign or paper signature, and return to the researcher and the other for the participant to keep. However, the participant is not obligated to keep the consent form. The participant is offered a copy to keep so they will have information about how to contact the research team with further questions and the IRB contact information. If participant chooses not to keep the consent form, they will be told that they can always request a consent form after release if they so choose. No aspect of the study will proceed until the consent process is completed. A researcher will inform participants that if they decide not to be in this study, or stop participating at any time, they will not be penalized or lose any benefits for which they otherwise qualify. A researcher will also inform participants that their sentence, program participation, employment opportunities, or any other aspects of their supervision by the DOC will not be affected by their choice to participate. Participants will be informed that their responses will be kept confidential to the fullest extent of the law. If a participant discloses they are the perpetrator or victim of sexual assault within the prison milieu, the incident will be addressed in accordance with PREA guidelines.

- 12.2 Participants receive \$30.00 for completing each of the three post-release interviews. The three follow-up interview timepoints are: (1) after the conclusion of the program period (post-test), (2) three

Commented [A2]: Add e-signature

months after the conclusion of the program period, and (3) nine months after the conclusion of the program period. Research participants will not get money for completing the baseline measurement packet while incarcerated.

